3.3 Selection of Study Population

3.3.1 Inclusion and Exclusion Criteria

Inclusion Criteria

Patients may be entered in the study only if they meet all of the following criteria.

1. Male or female patients ≥ 18 years of age;
2. Patients with histological confirmed BRAFV600E mutation+ melanoma (Stage IIIC or Stage IV, American Joint Commission on Cancer);
3. Eastern Cooperative Oncology Group (ECOG) Performance Status (PS) of 0 to 2;
4. Life expectancy ≥ 3 months;
5. At least 1 site of radiographically measurable disease by RECIST 1.1
6. Adequate hematologic, renal, and liver function as defined by laboratory values performed within 42 days prior to initiation of dosing:
 - Absolute neutrophil count (ANC) $\geq 1.0 \times 10^9/L$;
 - Platelet count $\geq 50 \times 10^9/L$;
 - Hemoglobin $\geq 8 \text{ g/dL}$;
 - Serum creatinine $\leq 2 \times$ upper limit of normal (ULN)
 - Total serum bilirubin $\leq 3 \times$ ULN;
 - Serum aspartate transaminase (AST/SGOT) or serum alanine transaminase (ALT/SGPT) $\leq 3 \times$ ULN, and $\leq 4 \times$ ULN if liver metastases are present.
7. Fertile males should use an effective method of contraception during treatment and for at least 3 months after completion of treatment, as directed by their physician;
8. Pre-menopausal females and females <2 years after the onset of menopause should have a negative pregnancy test at Screening. Pre-menopausal females must agree to use an acceptable method of birth control from the time of the negative pregnancy test up to 90 days after the last dose of study drug. Females of non-childbearing potential may be included if they are either surgically sterile or have been postmenopausal for ≥ 1 year;
9. Before study entry, written informed consent must be obtained from the patient prior to performing any study-related procedures.

Exclusion Criteria

Patients will not be entered in the study for any of the following:

1. Prior treatment with Vemurafenib or Dabrafenib;
2. Known hypersensitivity to Metformin or any of its components
3. Received radiotherapy for non CNS disease within the 2 weeks prior to commencing study treatment or have not recovered from side effects of all radiation-related toxicities to Grade ≤ 1 , except for alopecia;
4. Pregnant, breast-feeding, or refusing double barrier contraception, oral contraceptives, or avoidance of pregnancy measures;
5. Have any other uncontrolled infection or medical condition that could interfere with the conduct of the study.

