Clinical Study Protocol

Protocol Title: A Phase I/II Trial of Dabrafenib, Trametinib and Metformin Administered to Unresectable Stage IIIC and Stage IV BRAF^{V600E}+ Melanoma Patients

Protocol Number: BCC-MEL-14-01

Products: Dabrafenib, Trametinib and Metformin

Date of Protocol: April 30, 2014

Sponsor: James Graham Brown Cancer Center
University of Louisville
[name]
[name]

Principal Investigator: [name]., Ph.D.

Sub-Investigators: [name]., Ph.D.
[name]., Ph.D.
[name], M.B.B.S.

Study Statistician: [name].

SYNOPSIS

Name of Sponsor:	James Graham Brown Cancer Center
Name of Active Ingredients:	Dabrafenib, Trametinib and Metformin
Title of Study:	A Phase I/II Trial of Dabrafenib, Trametinib and Metformin Administered to Unresectable Stage IIIC and Stage IV BRAF ^{V600E} + Melanoma Patients
Protocol No.:	BCC-MEL-14-01
Investigators:	[name], [name], [name], [name], and [name]
Study centers:	James Graham Brown Cancer Center
Study duration:	Approximately 36 months
Objectives:	
Primary	
 • To evaluate the clinical activity of the FDA-approved drugs Dabrafenib (150 mg PO BID) and Trametinib (2 mg PO QD) in combination with Metformin (500 mg PO BID x 2 weeks, then 850 mg PO BID) in patients with unresectable BRAF^{V600E} positive Stage IIIC and Stage IV melanoma (Phase I). • To evaluate the clinical activity of the combined Dabrafenib/Metformin regimen (Phase II). • To monitor the safety profile of the combined regimen Dabrafenib/Metformin (Phase I/II) •
Secondary	
 • To estimate the overall survival of patients who have been treated with Dabrafenib, Trametinib and Metformin. • To describe the toxicities. • To explore the effect of other covariates (demographic, disease and treatment related) on objective response rate and toxicity and overall survival.

Number of patients:	A total of 53 patients are planned for the study.

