3.2.1 Screening

The patient must sign an Informed Consent Form (ICF) before any study procedures are performed. Screening procedures must be performed within 42 days of the first dose of study drug.

- Eligibility evaluation (review of inclusion/exclusion criteria);
- History of prior systemic treatment, including drug therapy and any other anti-cancer therapies such as radiation therapy;
- Demographic information (date of birth, gender, race, ethnicity);
- Determination of Stage IIIC or Stage IV disease; if Stage IV disease, document M1a/b/c;
- Relevant medical history and surgical history, including treatment history for melanoma and BRAF status;
- Vital signs (body temperature, respiratory rate, blood pressure, heart rate, height, and weight [kg]);
- Physical examination;
- Eastern Cooperative Oncology Group (ECOG) Performance Status (PS) (see Appendix);
- Clinical laboratory assessment (hematology and serum chemistry);
- Serum pregnancy test for female patients of childbearing potential;
- Tumor assessment (imaging), unless results are available from appropriate CT scans performed within 42 days prior to the initiation of Dabrafenib/Trametinib/Metformin. CT scans with contrast are preferred; the Investigator may authorize CT scans without contrast;
- Radiological assessment of the brain: All patients are required to have a CT scan with contrast or MRI scan of the brain, unless results from appropriate scans performed within 42 days are available;
- 2D-Echo or MUGA (in accordance with the manufacturer's package insert for Trametinib).
- Collection of AEs.

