4.9 Concomitant Medications

Concomitant medications and treatment (for example, palliative radiotherapy) during the study will be allowed at the Principal Investigator's discretion.

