There is no data available at the institution to support the sample size justification based on efficacy of this treatment combination. **In the published literature, the objective response rate to Dabrafenib and Trametinib using RECIST 1.1 Criteria is 76% (N=54, 95% CI, 65% to 87%)¹ (Flaherty et al, NEJM, 367:1694, 2012).** We expect that the overall response rate should be between 60-80%. Therefore an objective response rate less than 64% should indicate the treatment is not sufficiently promising ($P_0 = 0.64$); this is a bit lower than the lower limit of the 95% CI. We expect the therapy to increase the overall response rate at 80% ($P_1 = 0.80$). Using Simon's two stage minimax design for phase II trials we plan to enroll a maximum of 53 patients. In first stage, 20 patients will be enrolled. Table S1 gives the details of the justification of this sample size. Note that if the treatment is not altered in Phase I, patients enrolled on Phase I will be included in Phase II in the efficacy estimation.

Table S1. Sample size justification $P_0 = 0.64$, $P_1 = 0.80$, $\alpha = 0.05$ and power = 80%

MiniMax Two Stage Design	MiniMax Design
First Stage Sample Size (n1)	20
Upper Limit For 1 st Stage Rejection of Drug (# of OR)	13
Maximum Sample Size (n)	53
Upper Limit for 2 nd Stage Rejection of Drug (# of OR)	39
Expected Sample Size If Response Probability = 0.64	33
Probability of Early Termination at If RP=0.64	0.62

6.4 Accrual Rate:

Based on our experience we plan to enroll 30 patients per year. It will take approximately 2.0 years to complete the enrollment of 53 patients. Depending on the treatment's performance we may not need to enroll all 53 participants. Given the relatively short overall survival times, all patients will be followed for up to 3 years once enrolled and after the end of treatment with Dabrafenib/Trametinib/Metformin.

6.5 Statistical Analysis:

General Approach:

Patients receiving treatment will be presented. Patients receiving treatment who are found not to have fully met the eligibility criteria will be presented. On-study protocol violations will also be presented. Patients who do not complete the required observations will be listed and evaluated separately as necessary. Reasons for study discontinuation and date of withdrawal from study will be presented.

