Descriptive statistics related to the participant characteristics, treatment, and prognostic factors will be reported. Clinical response rates (complete, partial, and sustained) along with 95% confidence intervals will be estimated. The overall survival will be estimated by the Kaplan-Meier method²⁹. Differences in survival will be evaluated through the estimated hazard rates using the un-weighted log-rank tests. The OS time will be determined as the time from enrollment until death or last follow-up evaluation. In order to examine the significant prognostic factors, we will use the Cox proportional hazards regression models in both uni-variable and multi-variable setting³⁰. Descriptive statistics associated with the toxic events will be reported. The factors to be analyzed are ethnicity, gender, age, and pathological subtype. The various factors will be placed into categorical variables.

All calculations will be performed with SAS statistical software (SAS Institute Inc., Cary, NC). Analyses for specific aims are outlined below.

Statistical Analysis for specific aims:

Primary Objectives:

- *To evaluate the safety of the FDA-approved Dabrafenib and Trametinib in combination with Metformin in patients with unresectable Stage IIIC and Stage IV melanoma (Phase I).*

A total of 6 consecutive patients will be evaluated on this combination treatment. If any drug-related death occurs in this early stage, the study will be suspended. To continue on Phase II, at the most two drug-related CTCAE grade 4 events are allowed, which is in line with a Typical Phase I study with only one dose.

- *To estimate the efficacy of the Trametinib/Dabrafenib/Metformin regimen (Phase II).*

The efficacy will be estimated based on objective response (OR) rate, which is PR+ CR. We will estimate the OR rate along with its 95% confidence interval. We will also estimate CR and PR rates along with 95% confidence intervals. We will also compare these rates with published rates NEJM (2011)⁸ by comparing the confidence intervals.

- *To monitor the safety the combined regimens (Phase I/II).*

The monitoring rule is outlined in the next subsection.

Secondary Objective:

- *To estimate the overall survival rate on the combined regimes.*

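### Exclusion 1 leaves patients with prior trametinib, another MEK inhibitor or another BRAF inhibitor eligible, which may lower the response rate tested against the fixed 64%/80% design

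*Combined protocol and SAP*

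**What the plan says.** Sections 3.1.1 and 4.1 give every patient all three drugs. Exclusion 1 in section 3.3.1, repeated in the synopsis, bars "Prior treatment with Vemurafenib or Dabrafenib". Of the study drugs, only dabrafenib is named.

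No other provision closes the gap:

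- Exclusion 2 covers "Known hypersensitivity to Metformin or any of its components". It does not address current or past metformin use.
- Exclusion 5 is a catch-all for patients who "Have any other uncontrolled infection or medical condition that could interfere with the conduct of the study". It does not concern earlier drugs.
- Section 3.2.1 collects "History of prior systemic treatment, including drug therapy and any other anti-cancer therapies such as radiation therapy", but as a record, not an eligibility limit.
- Section 4.9 leaves other drugs to discretion: "Concomitant medications and treatment (for example, palliative radiotherapy) during the study will be allowed at the Principal" Investigator's judgment.
- Section 6.5 states that "The factors to be analyzed are ethnicity, gender, age, and pathological subtype". Prior targeted therapy and metformin use are not on that list.

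Section 6.3 rests the Phase II test on a published doublet result: "the objective response rate to Dabrafenib and Trametinib using RECIST 1.1 Criteria is 76"% (N=54, 95% CI 65% to 87%). From this it sets P0 = 0.64 and P1 = 0.80. The synopsis names the doublet given alone as the reference therapy.

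**The concern.** A single-arm trial compares its response rate with a fixed number, so a shift in case mix goes straight into the result. Section 6.1 describes the study as uncontrolled, and no concurrent arm would absorb such a shift. Patients whose disease has already been exposed to one of the regimen's targeted drugs, or to another drug of its class, may respond less often than the patients the sponsor had in mind when setting the 80% target. The protocol gives no reason for admitting them.

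The cost would be a higher chance of stopping after stage 1, or of missing the final threshold, when the regimen works as hoped in patients without that exposure. Table S1 leaves almost no spare power, so a few patients could matter.

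Metformin raises a different question. A patient already taking it at the baseline scan has not had it added during the study, which may confound the comparison with the doublet alone.

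**Working it through.** **Inputs from section 6.3 and Table S1.** P0 = 0.64, P1 = 0.80, n1 = 20, r1 = 13, n = 53, r = 39. The trial continues with at least 14 of 20 responses and succeeds with at least 40 of 53.

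**Formulas (exact binomial).**

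- Early termination: PET = P(X1 ≤ 13 | 20, p)
- Expected size: EN = 20 + (1 − PET) × 33
- Success: sum over x1 = 14 to 20 of P(X1 = x1 | 20, p) × P(X2 ≥ 40 − x1 | 33, p)

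**The plan's own figures.** At p = 0.64: PET 0.620, EN 32.6, type I error 0.047. At p = 0.80: PET 0.087, power 0.805. Table S1 states PET 0.62, expected size 33, alpha 0.05 and power 80%, so it reproduces.

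**Dilution model.** Let f be the share of pre-exposed patients and q their response rate, with the others at 0.80 and exposure falling at random across enrollment. Then p = 0.80(1 − f) + qf. Both f and q are assumptions. Shares of 5% and 10% correspond to about 3 and 5 of 53 patients (0.05 × 53 = 2.65; 0.10 × 53 = 5.3).

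The values q = 0.48 and 0.52 are the single-agent vemurafenib rates in section 1.2: 48% in the randomized trial against dacarbazine, and (3 + 66)/132 = 52% in the phase II trial. They are stand-ins for a patient in whom trametinib adds nothing further but the BRAF inhibitor is new. The values 0.20, 0.40 and 0.60 are illustrative.

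| q | p, f = 5% | power | p, f = 10% | power |
|---|---|---|---|---|
| 0.20 | 0.770 | 0.63 | 0.740 | 0.44 |
| 0.40 | 0.780 | 0.70 | 0.760 | 0.57 |
| 0.48 | 0.784 | 0.72 | 0.768 | 0.62 |
| 0.52 | 0.786 | 0.73 | 0.772 | 0.65 |
| 0.60 | 0.790 | 0.75 | 0.780 | 0.70 |

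At q = 0.20 and f = 10%, the chance of stopping at stage 1 rises from 0.087 to 0.247.

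**Direction.** Applying the same mix to the null, p = 0.64 × 0.90 + 0.20 × 0.10 = 0.596, and the success probability falls from 0.047 to 0.010. The error works against the drug.

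**The other rule.** Section 6.7 stops at 12 or fewer responses in 28 and requires at least 29 of 53. Its success probability is 0.93 at a true rate of 0.64 and above 0.99 at 0.74 to 0.80, so under that rule the dilution above makes no practical difference.

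**Metformin.** If a current user loses the whole metformin increment, that patient receives the doublet, for which section 6.3 gives 76%. With q = 0.76 and f = 5%, 10% and 15%, p = 0.798, 0.796 and 0.794, and power is 79.5%, 78.5% and 77.4%. The loss is 1 to 3 points.

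**The case against.** The strongest reply is that both drivers of the power loss are unknown. Anyone who has had the dabrafenib-trametinib doublet is already excluded through dabrafenib, so the remaining group may be small. A patient with trametinib alone has had neither dabrafenib nor vemurafenib and may still respond to the BRAF inhibitor. At the 48% to 52% rates, power is 72% to 73% at a 5% share and 62% to 65% at 10%. The 44% figure is the extreme of an assumed range, not an expectation. This stands.

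A reader might also infer that the exclusion contradicts the protocol's own account of resistance. Section 1.2 does not support that: it discusses resistance to BRAF inhibitors and presents MEK inhibition as a way around it, without discussing MEK-inhibitor resistance. The synopsis still has an objective worded "To evaluate the clinical activity of the combined Dabrafenib/Metformin regimen (Phase II"), which could suggest a list left over from a two-drug plan. That is conjecture, since section 2.1 names all three drugs. Nor does the protocol say that its 64% and 80% assume every component is new to the patient; it gives no prior-treatment criteria for the benchmark.

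A further tempting reading is that baseline metformin users dilute the response rate or carry no information. The documents do not support this. Section 1.2 reports more complete responses in diabetic breast cancer patients on metformin, and hypothesizes an effect of the combination, which these patients do receive. Assigning them 64% would use the null threshold in place of the published 76%.

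Finally, prior treatment is recorded, and section 6.5 promises to explore treatment-related covariates by regression. That helps description, but it names neither exposure and does not alter the stage 1 or final decision.

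**Conclusion.** The gap in Exclusion 1 is real: patients with prior trametinib, another MEK inhibitor or an unnamed BRAF inhibitor are eligible, and nothing elsewhere removes them. The harm is possible, not established. Under Table S1, and assuming 20% to 52% response in such patients, power falls from 80.5% to about 63% to 73% at a 5% share and 44% to 65% at 10%. The documents supply no share, and no response rate for these patients. The bias can hide a benefit but does not inflate false positives. The size holds only if Table S1 governs; under section 6.7 it is negligible. That does not excuse the criterion, because the 41% rate in section 6.7 does not match the 64% null of section 6.3.

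For metformin, the supported point is possible confounding of the comparison with the doublet alone. The narrow hypersensitivity exclusion is a separate matter and adds nothing to this one.

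**What to change.** - In section 3.3.1 and the synopsis, change Exclusion 1 to prior treatment with any BRAF or MEK inhibitor, including vemurafenib, dabrafenib or trametinib. This costs one line in two places, and a few pre-treated patients become ineligible.
- Record metformin use at baseline and pre-specify a sensitivity analysis of the response rate that leaves out baseline users. This costs one data item and one extra estimate; no patient needs to be excluded.
- Have the sponsor reconcile existing metformin use with the lead-in schedule in sections 3.1.1 and 4.1.
- Reconcile Table S1 with section 6.7 so that one decision rule applies, then restate the operating characteristics under it.

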Diagnosis and entry criteria:	
Exclusion Criteria
 
Patients will not be entered in the study for any of the following:
 
 1. Prior treatment with Vemurafenib or Dabrafenib 2. Known hypersensitivity to Metformin or any of its components; 3. Received radiotherapy for non CNS disease within the 2 weeks prior to commencing study treatment or have not recovered from side effects of all radiation-related toxicities to Grade ≤ 1, except for alopecia; 4. Pregnant, breast-feeding, or refusing double barrier contraception, oral contraceptives, or avoidance of pregnancy measures; 5. Have any other uncontrolled infection or medical condition that could interfere with the conduct of the study.
Test product, dose and mode of administration:	Dabrafenib (150 mg PO BID) and Trametinib (2 mg PO QD) in combination with Metformin (500 mg PO BID x 2 weeks, then 850 mg PO BID) until progression.
Reference therapy:	Dabrafenib and Trametinib without Metformin.
Duration of treatment:	
 • Pre-treatment phase: An up to 42-day Screening period for collection of Baseline assessments (scans prior to study enrollment may be used for baseline measurement); • Treatment phase: Treatment period of 28-day cycles until progression unless unacceptable toxicity; • Follow-up phase: Patients will be followed for survival for a period of up to 3 years.
Criteria for evaluation:	
Efficacy Assessments
 
Tumor response and disease progression will be determined by the Investigator using objective radiologic criteria (Investigator assessed review of CT scans). Disease response or progression will be determined according to RECIST 1.1. An MRI will be used only if CT scans are not appropriate or CT scan results are not conclusive.
 
Primary efficacy endpoint: RECIST 1.1 objective response rates
 
Secondary efficacy endpoint: Overall survival
 
Pharmacokinetic Not applicable.
 
Pharmacodynamic

Criteria for evaluation (continued):	Not applicable Safety Safety will be assessed by the monitoring and recording of all adverse events (AEs) and serious adverse events (SAEs), regular monitoring of hematology, blood chemistry, regular measurement of vital signs, and the performance of physical examinations.

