5.2.3 Tumor Assessments

Tumor measurements will be performed using RECIST 1.1. At a minimum, CT scans of the head, chest, abdomen, and pelvis will be performed at study entry, every 2 months while on treatment, following the last administration of the test agents, or at any time there is clinical evidence of disease progression, to evaluate disease status.

This section provides the definitions of the criteria used to determine objective tumor response for target lesions using RECIST 1.1.

Complete Response (CR): Disappearance of all target lesions. Any pathological lymph nodes (whether target or non-target) must have reduction in short axis to <10 mm.

Partial Response (PR): At least a 30% decrease in the sum of diameters of target lesions.

Progressive Disease (PD): At least a 20% increase in the sum of diameters of target lesions, taking as reference the smallest sum on study (this includes the baseline sum if that is the smallest on study). In addition to the relative increase of 20%, the sum must also demonstrate an absolute increase of at least 5 mm. (Note: the appearance of one or more unequivocal new metastatic lesions is also considered progression).

Stable Disease (SD): Neither sufficient shrinkage to qualify for PR nor sufficient increase to qualify for PD, taking as reference the smallest sum of diameters while on study.

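### The baseline scan may predate other anti-cancer treatment given before first dose, so shrinkage from that treatment can be scored as response to the triplet

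*Combined protocol and SAP*

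**What the plan says.** **Scan window.** Section 3.2.1 requires a screening tumor assessment "unless results are available from appropriate CT scans performed within 42 days prior to the initiation of Dabrafenib/Trametinib/Metformin". The synopsis, under duration of treatment, adds that "scans prior to study enrollment may be used for baseline measurement".

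**Washout.** Exclusion 3 (Section 3.3.1) excludes a patient who "Received radiotherapy for non CNS disease within the 2 weeks prior to commencing study treatment", or whose radiation toxicity has not recovered to Grade 1 or less. No interval is given for CNS radiotherapy. For drugs, Exclusion 1 bars "Prior treatment with Vemurafenib or Dabrafenib" outright, and no interval is given for any other agent. Screening collects "History of prior systemic treatment, including drug therapy and any other anti-cancer therapies such as radiation therapy", but no other criterion uses that history.

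**Lesions and response.** Inclusion 5 asks for "At least 1 site of radiographically measurable disease by RECIST 1.1". Section 5.2.3 defines partial response as "At least a 30% decrease in the sum of diameters of target lesions" and does not name the reference scan. It contains no rule for irradiated lesions.

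**On study.** Section 4.9 states: "Concomitant medications and treatment (for example, palliative radiotherapy) during the study will be allowed", at the Principal Investigator's discretion.

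**The concern.** The washout is counted back from first dose, and so is the scan window, but neither is tied to the other. Nothing requires the baseline scan to come after the last prior treatment. A trial run exactly as written can therefore measure a lesion, treat it with something else, start the triplet, and credit the combined shrinkage to the triplet.

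This matters because the primary endpoint is an investigator-assessed response rate in a single arm, judged against a fixed 64% (Section 6.3). No concurrent control would share the same carry-over and cancel it. The margin is also thin: under Table S1, success is 40 or more responses in 53, so one or two misattributed responses change the operating characteristics.

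There is a smaller safety counterpart. Section 6.8 counts grade 3 or 4 toxic events against Table S2 without saying that they must be drug-related. Late toxicity from an earlier therapy that appears after first dose could enter that count.

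**Working it through.** **1. Exposed window.** Inputs: scan at most 42 days before first dose (Section 3.2.1); non-CNS radiotherapy barred in the last 2 weeks (Exclusion 3).
- Non-CNS radiotherapy: 42 − 14 = 28, so about four weeks (roughly Day −41 to Day −15) can lie after the baseline scan.
- CNS radiotherapy and systemic drugs other than the two barred: no interval, so up to the full 42 days.

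**2. Effect on one patient.** PR needs the target sum to fall to 0.70 of its baseline value. If the sum has already changed by a factor k between scan and first dose, the further decrease needed on the triplet is 1 − 0.70/k.
- 10% prior shrinkage (k = 0.90): 1 − 0.70/0.90 = 22.2%.
- 20% prior shrinkage (k = 0.80): 1 − 0.70/0.80 = 12.5%.
- 10% prior growth (k = 1.10): 1 − 0.70/1.10 = 36.4%. This is the opposite bias.

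**3. The plan's own figures.** Table S1 rule: stop at 13 or fewer responses in 20; reject the drug at 39 or fewer in 53. With exact binomials, X1 ~ Bin(20, p) and X2 ~ Bin(33, p):
- Early stopping at p = 0.64: P(X1 ≤ 13) = 0.6197 (Table S1: 0.62).
- Expected N at 0.64: 20 + (1 − 0.6197) × 33 = 32.55 (Table S1: 33).
- P(declare success) = sum over x from 14 to 20 of P(X1 = x) × P(X2 ≥ 40 − x): 0.0467 at p = 0.64 and 0.8047 at p = 0.80 (Table S1: alpha 0.05, power 80%).

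Table S1 reproduces.

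**4. Carry-over.** Let s be the share of all true non-responders scored as responders because of other treatment. **s is an assumption; the documents give no value.** It is the product of the fraction of patients so treated and the share of their non-responders who are reclassified. The apparent rate at a true 64% is 0.64 + 0.36s, and the expected extra responses in 53 patients are 53 × 0.36 × s.

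| s (assumed) | apparent rate | extra responses in 53 | false-positive rate | early-stopping probability |
|---|---|---|---|---|
| 0 | 0.640 | 0 | 4.7% | 0.62 |
| 0.6% | 0.642 | 0.1 | 5.0% | 0.61 |
| 2.5% | 0.649 | 0.5 | 6.1% | 0.59 |
| 5% | 0.658 | 1.0 | 7.9% | 0.55 |
| 10% | 0.676 | 1.9 | 12.6% | 0.48 |

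The 0.6% row is, for example, 10% of patients treated in the window and 6% of their non-responders reclassified. The 6% is borrowed from the dacarbazine response rate in Section 1.2, for scale only.

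**5. Dependence on the decision rule.** Section 6.7 gives a conflicting rule: stop at 12 or fewer of 28; success at 29 or more of 53. Under it, the chance of success at a true 64% is already 0.93, so the table above does not apply. That conflict is a separate and larger problem.

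**The case against.** **The size rests on assumptions.** This stands. Neither the share of recently treated patients nor the carry-over effect is in the documents. The response rate quoted for dacarbazine is 6%, and the complete response rates in Section 1.1 for dacarbazine, interleukin-2 and ipilimumab are 1.5% to 6%. These do not estimate s directly, since carry-over may only top up shrinkage, but they point to small values. Response uses the sum over all target lesions, so one irradiated lesion changes a patient's category only if it weighs heavily in that sum. A reader might push s to 20% and quote a false-positive rate of 27.6%. The documents give no support for a value that high.

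**The direction is not fixed.** This also stands. A reader might infer that old scans can only add false responders. Untreated growth between an old scan and first dose hides true responses, as step 2 shows, so the net direction is not established.

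**Phase I is protected.** Largely so. A reader might infer that residual toxicity from earlier drugs will drive the 6-patient decision. Section 6.3 counts only drug-related grade 4 events and drug-related deaths, Section 5.3.1 requires a causality judgment on each event, and Section 5.3.1.1 keeps most events before first dose out of the record. Misattribution is possible, but the documents do not make it the expected outcome. Only the Table S2 count lacks the qualifier.

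**RECIST 1.1 may deal with irradiated lesions.** The protocol adopts RECIST 1.1 but reproduces only its response definitions. What the full criteria say cannot be settled from these documents. The protocol text has no such rule, and the scan and washout windows are its own.

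**Conclusion.** The gap is real: the stated windows let other anti-cancer treatment fall between the baseline scan and first dose, and nothing in the protocol text stops the resulting shrinkage, or shrinkage from on-study palliative radiotherapy, from being scored as objective response to the triplet. That is a possibility the plan leaves open, not a demonstrated inflation.

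The consequence is modest if few patients are affected. For the assumed shares of 0.6% to 10%, the false-positive rate under Table S1 is 5.0% to 12.6%, against 4.7% with none. About one misattributed response in 53 takes it to 7.9%. These figures hold only under the Table S1 rule, a true rate of 64%, and carry-over that is not offset by growth after an old scan. The safety part is limited to the Table S2 count. The point should be corrected because the remedy is cheap, not because a large bias has been shown.

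**What to change.** 1. In Section 3.2.1 and the synopsis, require the scan used as the response baseline to be taken after the last prior anti-cancer treatment (systemic, or radiotherapy including CNS) and before first dose. In Section 5.2.3, define PR against that scan.
2. In Section 5.2.3, state that a lesion irradiated before entry is not a target lesion unless growth since the radiotherapy is documented, and that shrinkage of a lesion irradiated on study does not count toward CR or PR.
3. Ask the sponsor to reconcile the washout windows in Exclusion 3 with the 42-day scan window. Any interval or toxicity-recovery threshold is a clinical matter for the sponsor, and none is proposed here.

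Cost: protocol wording, and a later-timed screening scan for a few recently treated patients. The treatment history needed to apply the rule is already collected at screening. A scan after the last treatment does not remove a delayed effect that continues past that scan, which is why item 3 is still needed.
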